## 1.2 Rationale

The Russian MoH has recently initiated a national program aimed to increase the proportion of HIV diagnosis and linkage to care of HIV infected individuals. Treatment durability is an important factor in HIV disease management since HIV infected individuals need to take ART for many years. [5] To date, there is limited data on treatment durability in HIV infected individuals initiating ART in Russia. Understanding the durability of treatment is essential for improving patient management in order to achieve the goals set by the Russian MoH and the HIV elimination goals set by the WHO.

According to the robust clinical studies data, there was significant increase of CNS AEs in groups of patients treated with EFV [14]. As with other NNRTIs, drug interactions and a low resistance barrier have to be considered. Novel NNRTIs such as etravirine and rilpivirine were implemented in routine clinical practice in Russia recently and have higher cost which may influence access and therefore durability to this third drug medications.

Observational studies, in contrast to clinical trials, have the potential to offer valuable additional information with respect to real-life settings, such as durability of the regimen over longer periods of time. Cohort studies have evaluated the reasons for change of first-line regimen in the short term [10, 18] and long term [19] and the prevalence of use of different NNRTIs and PIs in first-line [12]. Nevertheless, durability of first-line ART and prognostic factors (either positive or negative) measured in current study, such as the probability of requiring ART switch, may have significant economic and public health relevance. Also durability can be highly influenced by local circumstances. Therefore, in this study, the durability of initial ART will be evaluated according to the third component in a cohort from Russia and association of baseline patient characteristics with treatment durability over a long period of time will be explored.

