### 2.2 Secondary Objectives

- To evaluate the estimated time on therapy without change of the NNRTI or PI agent at 48 weeks among treatment naive HIV-infected individuals initiated ART (NNRTI, PI)
- To describe baseline clinical and demographic characteristics of treatment naive HIV-infected individuals initiated ART (NNRTI, PI)
- To assess association between clinical and demographic characteristics of patients and treatment durability at 48 weeks

- To evaluate the 96 weeks treatment durability among treatment naive HIV-infected individuals initiated ART (NNRTI, PI) determined as a percentage of patients remained on initial therapy without change of the NNRTI or PI agent
- To evaluate the estimated time on therapy without change of the NNRTI or PI agent at 96 weeks among treatment naive HIV-infected individuals initiated ART (NNRTI, PI)
- To assess association between clinical and demographic characteristics of patients and treatment durability at 96 weeks

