### **3.2 Study Population**

All patients enrolled must be treatment naive at the time of initiation of ART with NNRTI plus two NRTIs or PI boosted by ritonavir with 2 NRTIs per the usual standard of care of the investigator in AIDS clinics of Russia.

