### 4.2 Clinical Variables

The following clinical parameters will be retrospectively recorded at baseline:

- 1) HIV diagnosis duration at baseline (years);
- 2) Route of infection: IV drug use, homosexual (MSM), heterosexual, other;
- 3) HIV stage (if applicable): I-V;
- 4) Baseline viral load (copies/ml);
- 5) Baseline CD4 cells count (cells/µl);
- 6) Concomitant medications at baseline;
  - a. Data will be retrospectively captured on medication given for the treatment for any disorder/disease but HIV/AIDS at baseline

- 7) Comorbidities at baseline: No, Yes – CV disease, diabetes mellitus, CK disease, liver disease, viral hepatitis, pulmonary disease, tuberculosis, CNS disease, psychiatric disorder;
- 8) ART therapy: NNRTI plus two NRTIs; PI boosted by ritonavir with 2 NRTIs.

It should be noted that demographic and clinical variables collected in this non-interventional retrospective study are recommended for daily-practice clinical record keeping for the management of HIV-infection in Russia. Thus, these variables are available for the majority of the HIV-infected patients in regular clinical practice and can be collected within locally applicable legal and ethical framework for non-interventional research.

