#### **7.1.2 Secondary Objectives:**

- Time on therapy (weeks) without change of the NNRTI or PI agent at week 48 from the ART initiation will be presented in Kaplan-Meier plots
- Demographic and clinical characteristics at baseline will be presented descriptively by initial ART regimen (NNRTI or boosted PI plus 2 NRTIs) and overall
- Association between characteristics of patients and treatment durability at 48 weeks will be investigated via:
  - Subgroup analysis: number and percent of patients continuing treatment at 48 weeks will be presented descriptively by demographic and clinical characteristics categorized according to 8.1.4
  - Multivariate logistic regression analysis to identify potential risk factors for discontinuation of initial ART at 48 weeks. Demographic and clinical characteristics categorized according to 8.1.4 will be included into multivariate analysis only if they are found significant in univariate logistic regression analysis. Unadjusted (univariate model) and adjusted (multivariate model) odds ratios will be presented with 95% confidence intervals for the parameters included in each of the analyses.
- Percentage of HIV-infected patients remained on first-line ART at 96 weeks after the start of treatment will be presented descriptively with 95% confidence interval by initial ART regimen (NNRTI or boosted PI plus 2 NRTIs) and overall
- Time on therapy (weeks) without change of the NNRTI or PI agent at week 96 from the ART initiation will be presented in Kaplan-Meier plots
- Association between characteristics of patients and treatment durability at 96 weeks will be investigated via:
  - Subgroup analysis: number and percent of patients continuing treatment at 96 weeks will be presented by demographic and clinical characteristics categorized according to 8.1.4

- Multivariate logistic regression analysis to identify potential risk factors for discontinuation of initial ART at 96 weeks. Demographic and clinical characteristics categorized according to 8.1.3 will be included into multivariate analysis only if they are found significant in univariate logistic regression analysis ( $p<0.1$ ). Unadjusted (univariate model) and adjusted (multivariate model) odds ratios will be presented with 95% confidence intervals for the parameters included in each of the analyses.

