## 7.3 Sample Size and Power Calculations

There is no formal hypothesis testing the current study. Sample size justification is based on desired precision for the estimation of the primary variable – proportion of patients who continue the first line ART regimen at 48 weeks without changes.

The assumed 1-year discontinuation rate, based on published research, is 30% [20], therefore the assumed proportion of patients who remain on the first line ART regimen at 48 weeks is 70%. Precision (half-width of the 95% Wald confidence interval for the proportion) and 95% confidence intervals (CIs) for the proportion resulting from a range of sample sizes are presented in the table below:

Assumed Proportion	Patients enrolled	Patients with known status	95% CI Lower bound	95% CI Upper bound	95% CI Actual width (precision)
70.0%	250	250	64.3%	75.7%	11.4% ( $\pm 5.7\%$ )
70.0%	500	500	66.0%	74.0%	8.0% ( $\pm 4.0\%$ )
70.0%	750	750	66.7%	73.3%	6.6% ( $\pm 3.3\%$ )
70.0%	1000	1000	67.2%	72.8%	5.7% (<math>\pm 2.8\%</math>)
70.0%	1250	1250	67.5%	72.5%	5.1% ( $\pm 2.5\%$ )
70.0%	1500	1500	67.7%	72.3%	4.6% ( $\pm 2.3\%$ )

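### Univariate screening, with a p threshold stated only at week 96, can drop ART class or a masked confounder from the exploratory adjusted models at weeks 48 and 96

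*Combined protocol and SAP*

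**What the plan says.** Section 7.1.2 plans a "Multivariate logistic regression analysis to identify potential risk factors for discontinuation of initial ART at 48 weeks". Candidate characteristics "will be included into multivariate analysis only if they are found significant in univariate logistic regression analysis", with no significance level stated for week 48. The week-96 model follows the same rule: characteristics "categorized according to 8.1.3 will be included into multivariate analysis only if they are found significant", and there the level is p<0.1. Adjusted ORs are reported only for parameters that enter, so a variable that fails the screen has no adjusted estimate. No section forces any variable into either model.

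The candidate list is cited as 8.1.4 and 8.1.3. Section 8.1.3 concerns investigator confidentiality, and there is no 8.1.4. The evident target is Section 7.1.3, the category list in the statistical section. Its item 13 is regimen class, which Section 4.2 item 8 also lists as a clinical variable: "ART therapy: NNRTI plus two NRTIs; PI boosted by ritonavir with 2 NRTIs".

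Three other statements bear on the point. Section 1.2 says "the durability of initial ART will be evaluated according to the third component in a cohort from Russia". Section 3.2 says that patients started therapy "per the usual standard of care of the investigator in AIDS clinics of Russia". The secondary objective in Section 2.2 is "To assess association between clinical and demographic characteristics of patients and treatment durability at 48 weeks".

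**The concern.** The screen tests the crude association, which is the quantity that confounding distorts. Regimens were chosen in routine care, so class may be related to baseline severity or other characteristics. If patients at higher risk of discontinuing were more often given the class with the lower adjusted risk, the crude class difference shrinks and class may fail the screen. A confounder can be lost in the same way. The adjusted table then omits the dropped variable, and the ORs that remain absorb part of its effect.

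What is at stake is limited but specific. The by-regimen percentages and the unadjusted ORs cannot separate regimen class from patient characteristics; the adjusted model is the plan's only analysis that can. In addition, a week-48 threshold left open could be settled after results are seen, in data that already exist and with an interim analysis planned at 500 patients.

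**Working it through.** **The plan's own figure.** Section 7.3 sizes the study on precision: 1.96 × √(0.7 × 0.3 / 1000) = 0.0284, giving 67.16% to 72.84%. This agrees with the stated 67.2% to 72.8%. The plan gives no figure for the regression models.

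**The open threshold alone, without confounding.** For 30% versus 35% discontinuation and a PI share of 20–50% (both assumed), class passes the screen with probability 0.28–0.39 at p<0.05 and 0.39–0.52 at p<0.1. For 30% versus 40% the figures are 0.77–0.91 and 0.85–0.95. The choice of level shifts the chance of entry by about 4 to 12 points.

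**Masking: inputs.** From Section 7.3: N=1000, and "The assumed 1-year discontinuation rate, based on published research, is 30" per cent. Assumed, because the documents are silent: 40% of patients with low CD4, and a PI-versus-NNRTI OR between 0.5 and 0.9. Mild opposing channelling means PI in 40% of low-CD4 patients and 20% of others, with low-CD4 OR 1.5. Strong opposing channelling means 50% versus 20%, with low-CD4 OR 2.0.

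**How the crude OR shrinks (mild, class OR 0.67).**
- PI share: 0.4×0.4 + 0.6×0.2 = 0.28.
- Low CD4 among PI patients: 0.16/0.28 = 0.571. Among NNRTI patients: 0.24/0.72 = 0.333.
- Solving the intercept for 30% overall gives risks of 0.287 (NNRTI, other), 0.377 (NNRTI, low CD4), 0.213 (PI, other) and 0.288 (PI, low CD4).
- Crude PI risk: 0.571×0.288 + 0.429×0.213 = 0.256. Crude NNRTI risk: 0.333×0.377 + 0.667×0.287 = 0.317.
- Crude OR: (0.256/0.744)/(0.317/0.683) = 0.74, against the true 0.67. In the strong case it is 0.85.

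**Simulation.** Logistic models with Wald tests, 3000 to 4000 datasets per scenario, repeated with different seeds. A loss is counted when the crude class p fails the screen although p<0.05 for class in the class-plus-CD4 model. Losses in % (screen 0.1 / screen 0.05), with the spread over repeat runs:

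| Class OR | Mild opposing | Strong opposing |
|---|---|---|
| 0.5 | 1 / 2–3 | 8–9 / 14 |
| 0.67 | 9–11 / 22–24 | 41–44 / 50–53 |
| 0.8 | 8 / 15–16 | 23–25 / 25–27 |
| 0.9 | 4 / 6–7 | 9–10 / 9–10 |

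Without channelling, or with confounding that runs with the class effect, the loss is about 0–2%. With class OR 1.25 or 1.5 and the same channelling it is about 0%. At 40% discontinuation (assumed for week 96, where the plan gives no rate) and class OR 0.67, it is about 10 / 22 (mild) and 45 / 55 (strong).

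**The other adjusted ORs (class OR 0.67).** Low CD4 is itself screened out although its adjusted p<0.05 in about 6 / 16% under mild opposing channelling. Leaving class out moves the low-CD4 OR from 1.50 to 1.39 (mild) or from 2.00 to 1.77 (strong).

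**The case against.** The strongest reply has four parts.

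1. **The study is descriptive.** Sections 7.1.4 and 7.3 disclaim hypothesis testing, and the model searches for risk factors. A reader might infer that the plan promises an adjusted or causal NNRTI-versus-PI contrast and fails to deliver it. The documents do not support that: the objectives concern patient characteristics, and the rationale's reference to the third component is met by the by-regimen percentages with confidence intervals. Baseline tables by regimen would also reveal channelling. This stands and limits the weight of the point. It does not remove it, because the plan itself makes significance the gate for entry and lists class among the candidates.

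2. **The size depends on what is assumed.** Loss needs confounding that opposes the class effect, and the documents do not say who received which class. Of the class ORs tried, 0.67 gives the largest loss. The pooled analysis of 29 trials cited in Section 1.1 found no statistically significant class difference in discontinuation; that does not prove an OR of 1, but no document supports 0.67. Scenarios built so that masking is complete drop class in about 89–96% of datasets. It is tempting to read that, or the 40–50% cells above, as the expected loss. They show the mechanism and not its likelihood here.

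3. **The covariate list is partly preference.** This stands. Site, for example, could be argued for, since up to 8 sites are planned and Section 1.2 mentions local circumstances. Keeping a screen for the remaining factors leaves some of the same weakness in place.

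4. **The precision cost can exceed the simplest estimate.** This also stands, since route of infection and substance abuse overlap.

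**Conclusion.** The concern holds in a limited form. The entry rule, its use at both weeks, the missing week-48 threshold and the absence of any forced variable are plain in the text and need no assumption. That the rule can drop class or a confounder and bias the remaining adjusted ORs is a real property of it, conditional on channelling that opposes the class effect.

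With N=1000, 30% discontinuation, 40% low CD4 and class OR 0.5 to 0.9, the loss is about 1–10% (screen 0.1) or 2–23% (screen 0.05) under mild opposing channelling. Under strong opposing channelling it is about 9–42% or 9–52%, and otherwise about 0–2%. Which case applies cannot be told from the documents.

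A reader might conclude that the study's durability results are compromised. They are not. The primary proportion, the by-regimen percentages, the Kaplan-Meier plots, the subgroup tables and the unadjusted ORs do not depend on this rule. Only the secondary exploratory adjusted ORs do. This is a worthwhile, inexpensive improvement to the plan.

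**What to change.** **Change to Section 7.1.2, identical at both weeks.**
- Enter initial ART class and one short set of already collected baseline covariates regardless of univariate p, and fix the set before outcomes are examined. For example: age, gender, CD4 (≤200, 201–350, >350), viral load, route of infection, substance abuse and any comorbidity (yes/no). Merge sparse levels by a rule on patient counts.
- Allow the remaining 7.1.3 characteristics to be added at univariate p<0.1, with that level stated at both weeks. This keeps the broader risk-factor objective.
- Report the patients and events used in each adjusted model.
- Editorial: correct the references to 8.1.4 and 8.1.3 to 7.1.3.

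**Cost.** Wording only, no new data. The example set has 1 (class) + 2 + 1 + 2 + 2 + 3 + 2 + 1 = 14 terms, so 300/14 = 21 events per term at week 48. If gender keeps three levels it is 300/15 = 20. If all five remaining factors entered (18 more terms) it would be 300/32 = 9.4.

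The class standard error rises from 0.158 to 0.160, about 1%, with complete data and independent null covariates, and by more if covariates are correlated. If 10% or 20% of records lack a forced covariate (assumed), it is 0.169 or 0.180, about 7% or 14% larger, and events per term fall to 270/14 = 19 or 240/14 = 17. Part of that loss would also occur under the screened model, which loses incomplete records too.

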### 7.1.3 Subgroup analysis

The study population will be divided to several subgroups based on the baseline demographic and clinical characteristics. The following categories will be used for the subgroup analysis:

- 1) Age: < 40, 40-60, > 60 years;
- 2) Gender: male, female, transgender;
- 3) Employment status: employed, unemployed, student, pensioner, incarcerated;
- 4) Marital status: married, single, divorced;
- 5) Substance abuse: no, alcohol, drugs;
- 6) HIV diagnosis duration at baseline: 0-0.5, 0.5-1, 1-2, 2-3, 3-5, >5 years;
- 7) Route of infection: IV drug use, homosexual (MSM), heterosexual, other;
- 8) HIV stage (if applicable): I-V;
- 9) Baseline viral load: <50 000, 50 000-100 000, >100 000 copies/ml;
- 10) Baseline CD4 cells count: <50, 50-100, 101-200, 201-350 and >350 cells/ $\mu$ l;
- 11) Concomitant medications at baseline: 0, 1-2, 3-5, >5;
- 12) Comorbidities at baseline: No, Yes CV disease, diabetes mellitus, CK disease, liver disease, viral hepatitis, pulmonary disease, tuberculosis, CNS disease, psychiatric disorder;
- 13) ART therapy: NNRTI plus two NRTIs; PI boosted by ritonavir with 2 NRTIs.

### 7.1.4 Interim Statistical Analysis

Interim Statistical Analysis will be performed when data retrospectively collected from at least 500 patients during the first 6-9 months of the study. Since this observational study is not aimed at testing any hypothesis, no adjustment on significance level will be applied.

## 7.2 Bias

Potential sources of bias are errors in recruitment.

### 7.2.1 Methods to Minimize Bias

Bias from errors in recruitment of patients can be reduced with rigorous adherence to inclusion/ exclusion criteria when recruiting patients for the study.

### 7.2.3 Limitations

In this a retrospective study the quality of the data is important. And the potential issue of missing data is a limitation of the study.

Therefore, it is important for the sponsor or designee to monitor data completion and perform quality checks during the study. To minimize missing data, a set of core variables is required to be available at enrollment as part of inclusion criteria.

There is a risk that patients who had already been receiving ART might be enrolled due to unavailable medical records from his/her previously clinic which is not a part of the study.

## 7.3 Sample Size and Power Calculations

There is no formal hypothesis testing the current study. Sample size justification is based on desired precision for the estimation of the primary variable – proportion of patients who continue the first line ART regimen at 48 weeks without changes.

The assumed 1-year discontinuation rate, based on published research, is 30% [20], therefore the assumed proportion of patients who remain on the first line ART regimen at 48 weeks is 70%. Precision (half-width of the 95% Wald confidence interval for the proportion) and 95% confidence intervals (CIs) for the proportion resulting from a range of sample sizes are presented in the table below:

Assumed Proportion	Patients enrolled	Patients with known status	95% CI Lower bound	95% CI Upper bound	95% CI Actual width (precision)
70.0%	250	250	64.3%	75.7%	11.4% ( $\pm 5.7\%$ )
70.0%	500	500	66.0%	74.0%	8.0% ( $\pm 4.0\%$ )
70.0%	750	750	66.7%	73.3%	6.6% ( $\pm 3.3\%$ )
70.0%	1000	1000	67.2%	72.8%	5.7% (<math>\pm 2.8\%</math>)
70.0%	1250	1250	67.5%	72.5%	5.1% ( $\pm 2.5\%$ )
70.0%	1500	1500	67.7%	72.3%	4.6% ( $\pm 2.3\%$ )

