## PROTOCOL SUMMARY

Title	Retrospective evaluation of treatment durability among treatment-naive HIV-infected individuals initiated first-line ART in Russia
Supplier	Atlant Clinical Ltd
Rationale	Treatment durability is an important factor in HIV disease management since HIV infected individuals need to take ART life-long. To date, there is limited data on treatment durability in HIV infected individuals initiating ART in Russia. Understanding the durability of treatment is essential for improving medical care of patient living with HIV.
Primary Objective	To evaluate the 48 weeks treatment durability among treatment naive HIV-infected individuals determined as a percentage of patients remained on initial therapy
Study Design	A non-interventional retrospective study.
Study Population	Treatment-naive at the time of initiation of ART with NNRTI plus two NRTIs or PI boosted by ritonavir with 2 NRTIs per usual standard of care of the investigator in AIDS clinics of Russia.
Study Duration	Up to 24 months will be dedicated to retrospective data collection and analysis from treatment-naïve HIV-infected patients who initiated their first-line ART between February 01 and June 30, 2017
Exposure and Outcome	Initial ART per usual standard of care in AIDS clinics of Russia: NNRTI plus 2 NRTIs or PI boosted by ritonavir with 2 NRTIs. Treatment durability determined as a percentage of patients continuing their first-line for 48 and 96 weeks without changes (switch or withdrawal) evaluated retrospectively
Statistical Methods	Data will be presented descriptively as follows: the number of observations, mean and standard deviation, median, first and third quartiles, minimum and maximum for continuous variables, and the absolute frequencies and percentage of patients presenting the given feature for qualitative variables. The results on the study endpoints (proportion of patients who remain on first-line ART at 48 and 96 weeks) will be presented with two-sided 95% confidence intervals. Univariate and multivariate logistic regression will be used to study the association between patients' baseline demographic and clinical characteristics and treatment discontinuation status.

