## 2 Objectives and Hypotheses

### 2.1 Primary Objective

- To evaluate the 48 weeks treatment durability among treatment naive HIV-infected individuals initiated ART (NNRTI, PI) determined as a percentage of patients remained on initial therapy without change of the NNRTI or PI agent

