### 4.3 Outcomes

#### 4.3.1. Treatment Durability

Treatment durability is determined as a percentage of patients continuing their first-line ART with NNRTI plus 2 NRTIs or PI boosted by ritonavir with 2 NRTIs for 48 and 96 weeks without change of the NNRTI or PI agent (“anchor” or “third agent”) within the class or without change of the NNRTI or PI agent to a different class.

According to the Primary objective, the treatment durability is to be retrospectively evaluated at 48 weeks from the time of initiation.

According to the Exploratory objective, the treatment durability is to be retrospectively evaluated at 96 weeks from the time of initiation.

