#### **7.1.1 Primary Objective:**

- Percentage of HIV-infected patients remained on first-line ART at 48 weeks after the start of treatment will be presented descriptively with 95% confidence interval by initial ART regimen (NNRTI or boosted PI plus 2 NRTIs) and overall

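### Do the Protocol Summary and section 7.3 set a different primary endpoint from sections 2.1 and 4.3.1 when only an NRTI is replaced?

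*Combined protocol and SAP*

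**What the plan says.** Two places describe the endpoint without naming the component that must stay the same. Section 7.3 gives the primary variable as the "proportion of patients who continue the first line ART regimen at 48 weeks without changes". The Exposure and Outcome row of the Protocol Summary speaks of patients continuing their "first-line for 48 and 96 weeks without changes (switch or withdrawal"), and its Primary Objective row stops at "individuals determined as a percentage of patients remained on initial therapy".

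The body of the protocol is more specific. Section 2.1 has the "percentage of patients remained on initial therapy without change of the NNRTI or PI agent". Section 4.3.1 (Treatment Durability), which defines the outcome, says "for 48 and 96 weeks without change of the NNRTI or PI agent". It calls that drug the anchor or third agent, and it covers changes within the class and to another class.

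The analysis sections are mixed. Section 7.1.1 reports the "Percentage of HIV-infected patients remained on first-line ART at 48 weeks after the start of treatment" and does not say which component counts. Section 7.1.2 plots "Time on therapy (weeks) without change of the NNRTI or PI agent at week 48", and its logistic regression refers to discontinuing initial ART.

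**The concern.** The regimen has three components: an NNRTI or boosted PI, plus two NRTIs. If any change ends durability, replacing one NRTI with another is a failure. If only a change of the NNRTI or PI counts, the same patient is a success. No sentence in the documents says outright how that patient is classified, and neither the summary nor 7.3 points to 4.3.1.

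This touches the primary percentage. Under section 5.3 the electronic form is built from the protocol, and up to 8 sites classify patients from charts. Two readings could in principle lead sites to classify alike patients differently. They could also give the percentage, the Kaplan-Meier curve and the regression different events, or produce a report that presents third-agent durability as durability of the whole regimen.

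**Working it through.** **Step 1: the plan's own figure.** Inputs from 7.3 are an assumed proportion p = 0.70, n = 1000 and a two-sided 95% Wald interval.

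Half-width = 1.96 × √(p(1 − p)/n) = 1.96 × √(0.70 × 0.30/1000) = 2.84 points.

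The interval is 67.16% to 72.84% and the width 5.68 points. This agrees with the stated 67.2%, 72.8% and 5.7% (±2.8%). The other five rows of the table also reproduce.

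**Step 2: where the two wordings part.** Sections 2.1 and 4.3.1 require the patient to remain on or continue therapy, as well as to keep the third agent. Stopping all ART is therefore a failure under either wording, and so is a change of the NNRTI or PI. The readings differ only for patients whose change is confined to the NRTIs.

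**Step 3: which wording governs.**

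| Place | What it names |
|---|---|
| 2.1 and 2.2, objectives | NNRTI or PI agent |
| 3.1, instruction to investigators at 48 and 96 weeks | NNRTI or PI agent, within or across class |
| 4.3.1 Treatment Durability, the definition | NNRTI or PI agent |
| 4.3.1 Time on therapy | NNRTI or PI agent |
| Section 5, Study Procedures table | NNRTI or PI continuation; no NRTI item at follow-up |
| 7.1.2, Kaplan-Meier lines | NNRTI or PI agent |
| 7.1.2, regression | discontinuation of initial ART, under a parent bullet on treatment durability, the term 4.3.1 defines |
| 7.1 and 7.1.1 | first-line ART, component not named |
| Protocol Summary and 7.3 | no changes, component not named |

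The sections that define the outcome, instruct the sites and list the data items all agree. The summary and 7.3 do neither job. Section 7.1.1 is headed as the analysis of the primary objective, and 2.1 states that objective with the qualifier. No passage says that an NRTI replacement is a failure, and the listed follow-up items would not clearly support such a rule.

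**Step 4: what a different reading could move.** Let x be the share of patients who keep the third agent to week 48 but have an NRTI replaced. The documents do not give x. The two readings differ by exactly x.

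- At n = 1000, x exceeds the half-width of 2.84 points (28.4 patients) from 29 patients upward.
- At the interim analysis, n = 500, the half-width is 1.96 × √(0.21/500) = 4.02 points (20.1 patients), so the count is 21.
- Assuming x = 5% for illustration: if 70% were the rate with no change of any kind, the third-agent rate would be 75% (72.3% to 77.7%). If 70% were the third-agent rate, the other would be 65% (62.0% to 68.0%).

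**Step 5: precision.** The Wald half-width is largest at p = 0.50: 1.96 × √(0.25/1000) = 3.10 points. That is 0.26 points above the planned 2.84, whichever definition is used.

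**The case for a change.** The best case for amending the text is that an endpoint should be worded once and repeated identically. The summary is the part most often read. It adds its own gloss on what a change is, which a chart reviewer could apply to any drug in the regimen. Section 7.1.1, where the primary analysis is specified, does not close the gap, and an alignment would cost only a few words.

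Part of this stands. The summary and 7.3 are loosely worded, 7.1 and 7.1.1 are abbreviated, and results should be reported as durability of the third agent.

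The claim of inconsistent classification across sites does not stand. The sentence in 3.1 that tells investigators what to look for goes on to give the third-agent rule, and the procedures table follows it. The supposed split inside 7.1.2 does not stand either, because the regression is listed as a way of studying treatment durability.

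Two details stay open. Section 4.3.1 also speaks of "continuing their first-line ART with NNRTI plus 2 NRTIs or PI boosted by ritonavir with 2 NRTIs", so the status of a patient who drops an NRTI without replacement is not explicit. Counting that as an event could need a follow-up item that the table does not list. The documents also do not say which changes the 30% planning rate counts. That rate sets only the assumed level. For p between 0.55 and 0.85 the half-width at n = 1000 runs from 3.08 to 2.21 points.

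**Conclusion.** This is a clerical slip that the documents themselves resolve, and it calls for no change to the plan. Applying the plan as written gives the third-agent percentage. Bringing the summary and 7.3 into line would leave that percentage, the main data items, the planned analyses and N = 1000 as they are. There is no hypothesis test for the wording to affect.

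The 29 of 1000 and 21 of 500 are break-even counts for a reading that the plan does not support, not estimates of an error. The conclusion rests on 4.3.1 governing as the defining section, and on the form following the items listed in section 5. The 3.10-point ceiling also assumes that all 1000 statuses are known. If the form in fact recorded any NRTI replacement as a failure, the point would have to be reopened; nothing in the documents suggests that it does. An NRTI dropped without replacement is a detail for the sponsor to settle when the form is built.
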